**Table 4. Schedule of interventions and of monitoring patient outcomes.**

Outcome	Measure	Month of Study			
		0	3	6	12
Primary	Pain interference (PROMIS)	X	X	X	X
Secondary	Daily pain intensity (mobile app)	X	X	X	X
	Quality of life (ASCOQ-Me), depression (PHQ-9), anxiety (GAD-7), Painimation	X	X	X	X
	Opioid Use (COMM)	X			X
Medical	Health care utilization (PCORnet): Opioid prescriptions, ED visits, hospitalizations				X
Process Evaluation	Coping (CSQ), Self-efficacy (SCSES)	X	X	X	X
	Program engagement (treatment dose)		X		

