## 9 STATISTICAL CONSIDERATIONS

### 9.1 STATISTICAL HYPOTHESES

*State the formal and testable null and alternative hypotheses for primary and key secondary endpoints, specifying the type of analysis (e.g., feasibility/acceptability, efficacy, effectiveness, implementation) and time period for which each endpoint will be analyzed. Include this information for each hypothesis being tested, if multiple hypotheses are present. If the study is intended as a feasibility or pilot study, please consider that a formal hypothesis may not be available at the time of protocol writing. If so, include a statement indicating that hypotheses will be generated or that descriptive statistics only will be calculated.*

- Primary Efficacy Endpoint(s): Pain interference
  - $H_0$ : 6-month change in pain interference will not differ between the two intervention arms
  - $H_1$ : 6-month change in pain interference will differ between the two intervention arms
- Secondary Efficacy Endpoint(s): Pain intensity, depressive symptoms, health care utilization (opioid prescriptions, acute care visits) and opioid misuse behaviors (Current Opioid Misuse Measure – COMM)

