Linear mixed models will be employed for the primary outcome of pain interference as a function of time, study arm (digital CBT vs Education), time \times study arm interaction, study site, and baseline depression level (PHQ-9 \leq 10 vs PHQ-9 $>$ 10). We will account for multiple observations for each participant by including a random effect for the subject. In addition, baseline variables with large, clinically meaningful between-arm differences will be included as covariates in the secondary analyses. Contrasts will be estimated to assess the impact of digital CBT and education intervention on 6-month improvements in pain interference. As a secondary investigation, we will use the same linear mixed models to address whether the 6-month improvements are sustainable for 12 months. The analytic strategy for the key secondary outcome of pain intensity will be identical to that of the primary outcome. As the confirmation of a sickle cell diagnosis may not be made immediately after randomization, we will conduct an a priori sensitivity analysis restricting eligible participants with the confirmation of SCD.

Analysis of Secondary Outcomes

Secondary outcomes such as PHQ-9, Current Opioid Misuse Measure, GAD-7, Adult Sickle Cell Quality of Life Measurement Information System, and SCSES will be analyzed using similar linear mixed models with time, study arm, time×study arm interaction, study site, and baseline depression level as fixed covariates and a random effect for each subject. Health care use will be compared between study arms using generalized linear models to account for count data (i.e., Poisson regression) for each of the following: the number of opioid prescriptions, number of emergency department visits, and number of hospitalizations over 12 months after study entry. Predictors will include the study arm, study site, and baseline depression level. The corresponding health care use in the 12 months before study entry will be entered as a covariate in each model. We will offset each model by the participant's time in the study.

Subgroup Analysis

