We will examine the heterogeneity of the treatment effect to determine whether the intervention works better for some than for others. Our prespecified analysis plan will examine differences in pain interference between patients with high (PHQ-9>10) and low (PHQ-9≤10) depression. We will augment the primary analysis models for pain interference with relevant main effects for the baseline depression level and 2- and 3-way interactions with the study arm and time. Of primary interest is the significance of the 3-way interaction (time×study arm×baseline depression level). If significant, we will present the treatment effect estimates and 95% CIs within each subgroup. For all of the above-described models, we will focus on the 6-month outcome.

Mediation Analysis

For coping skills, self-efficacy, and program engagement or dose measures, changes in scores from baseline to 3 months and from baseline to 6 months will be tested as potential mediating variables. We will use the framework of Kraemer et al to calculate effect sizes, accounting for the impact of the potential mediator variable. In addition to modeling each mediator as a function of time, study arm, time×study arm interaction, study site, and baseline depression level (PHQ-9≤10 vs PHQ-9 >10), we will augment the original primary analytic models by including the potential mediator as a covariate.

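### As most naturally read, the mediation model adds a fixed change score that drops out of the 6-month arm contrast, and the 6-month mediator change is concurrent with the outcome

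*SAP*

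**What the plan says.** The SAP's Mediation Analysis paragraph names coping skills, self-efficacy and program engagement or dose, and states that "changes in scores from baseline to 3 months and from baseline to 6 months will be tested as potential mediating variables". It cites a published moderator-mediator framework for effect sizes and gives no formula. One sentence then describes two models. Its first half concerns the mediator as a response: "In addition to modeling each mediator as a function of time, study arm", together with the time-by-arm interaction, site and baseline depression group. Its second half concerns pain: "we will augment the original primary analytic models by including the potential mediator as a covariate". No mediator-by-time term, indirect-effect formula or decision rule is written.

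The SAP's section Analysis of Primary and Secondary Pain Outcomes gives the model to be augmented: "Linear mixed models will be employed for the primary outcome of pain interference as a function of time, study arm (digital CBT vs Education), time". That sentence goes on to the time-by-arm interaction, site and baseline PHQ-9 group; baseline pain is not among the terms. The SAP adds: "We will account for multiple observations for each participant by including a random effect for the subject". The target is 6-month change: "Contrasts will be estimated to assess the impact of digital CBT and education intervention on 6-month improvements in pain interference". Protocol 9.1 states the matching null: "6-month change in pain interference will not differ between the two intervention arms".

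On timing, the SAP's Study Outcomes section schedules pain interference and the self-efficacy scale at baseline, 3, 6 and 12 months. Protocol Table 4 gives the same four visits for coping. The Table 4 row that begins "Program engagement (treatment dose" carries one mark, apparently at month 3, and Protocol 6.1.2 measures engagement over the first 12 weeks. Protocol 9.4.9 lists mediation as exploratory.

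**The concern.** A change score takes one value per participant. Added as a main effect to a model with a random subject intercept, it raises or lowers that participant's pain at every visit by the same amount. The contrast of interest is a difference between visits, so a constant shift cannot explain it. An analyst who compares the arm effect with and without the mediator could then see no difference and report no mediation, even if the whole benefit ran through the mediator.

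Two further problems do not depend on the model. For the 6-month outcome, the 0-6 month mediator change is taken at the same visit, so the data cannot show which came first. And engagement cannot have a change from baseline if it is only measured once treatment is under way.

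At stake is the trial's account of mechanism. Protocol 4.1 (process evaluation measures) rests the intervention's effect on patients using the program and acquiring coping skills or knowledge.

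**Working it through.** **No figure to reproduce.** The plan states no power, effect size or expected share for mediation. The trial's power statement does not enter this point.

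**1. Algebra.** Write the primary model with a fixed mediator M as

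Y(i,t) = τ(t) + α·A(i) + δ(t)·A(i) + site + depression + γ·M(i) + u(i) + e(i,t), with δ(0) = 0.

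Subtract baseline from month 6:

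Y(i,6) − Y(i,0) = [τ(6) − τ(0)] + δ(6)·A(i) + [e(i,6) − e(i,0)].

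The term γ·M(i) is gone, as are u(i), site and depression. With complete data the estimate of δ(6) is the arm difference in mean change, whatever γ is. If M varies by visit, γ·[M(i,6) − M(i,0)] remains. If M is fixed but has a time-specific slope, [γ(6) − γ(0)]·M(i) remains. In either case δ(6) can change.

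**2. Simulation.** From the documents: N = 350, 1:1 allocation, visits at 0, 3, 6 and 12 months, random intercept, site and depression group. Assumed, because the documents give no values: arm effect on the mediator 0.5; effect of the 0-3 month mediator change on pain at each follow-up visit −0.6; no direct arm effect; all between- and within-person SDs 0.7. The true 6-month effect is 0.5 × (−0.6) = −0.30, all of it mediated. There were 25 datasets, fitted by REML. The mean standard error of the contrast is 0.115, so the simulation error of a mean is about 0.115/√25 = 0.023.

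Mean 6-month arm effect, complete data; share explained = 1 − adjusted/unadjusted:

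| How the mediator enters | Unadjusted | Adjusted | Share |
|---|---|---|---|
| Fixed 0-3 month change, main effect | −0.265 | −0.265 | 0% |
| Fixed 0-6 month change, main effect | −0.265 | −0.265 | 0% |
| Fixed 0-3 month change plus mediator-by-arm, no time term | −0.265 | −0.265 | 0% |
| Time-varying change | −0.265 | −0.137 | 48% |
| Fixed 0-3 month change, contrast is the month-6 level | −0.300 | −0.080 | 73% |
| Fixed 0-3 month change, follow-up visits only, baseline pain as covariate | −0.285 | +0.005 | 102% |
| Fixed 0-3 month change with mediator-by-time | −0.265 | +0.019 | 107% |

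In the first three rows the largest difference in any dataset was about 1e-14, which is rounding error. Shares above 100% are simulation noise around total mediation.

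**3. Missing data.** With about 13% missing at 6 months, dependent on baseline pain, the fixed 0-3 month score moved the contrast from −0.260 to −0.259. The shift was 0.004 on average and 0.012 at most, against about 0.26 to be explained. With mediator-by-time the contrast went to +0.026. For the 0-6 month score, among participants with an observed month 6, it did not move (below 1e-14). A separate run of 30 trials with n = 300 and 25% of visits missing gave −0.383 unadjusted, −0.384 with the main effect and −0.023 with mediator-by-time.

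**4. Which reading is natural?** The Subgroup Analysis paragraph, directly above, also augments the primary model and there names its 2- and 3-way interactions with arm and time. The mediation paragraph names none.

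**5. Timing.**

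| Mediator | 0-3 month change against 6-month outcome | 0-6 month change against 6-month outcome |
|---|---|---|
| Self-efficacy | precedes | same visit |
| Coping (Table 4) | precedes | same visit |
| Engagement | no baseline: no change score | no baseline or month-6 value: no change score |

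For coping this relies on Table 4. Protocol 4.1 and 8.1 also describe coping items being asked in the app as participants progress, and the SAP gives no coping schedule.

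**The case against.** A reader might infer that the planned analysis is incapable of finding mediation, or that the trial will report that coping, self-efficacy and engagement mediate nothing. The documents do not support that, for four reasons.

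- **Time-varying reading.** The same SAP sentence models each mediator over time with a time-by-arm term, which a single value per person does not permit. The covariate may therefore be meant as time-varying. In a variant run (25 trials, N = 350, assumed effects) with the whole effect passing through the mediator at the same visit, a time-varying covariate took the contrast from −0.302 to −0.001, while a fixed change score left it at −0.302.
- **Baseline as a response is inferred.** The SAP does not say so. With baseline pain as a covariate, or a month-6 level as the contrast, the estimate moves (table above).
- **The decision rule is not stated.** Neither document says that mediation is judged by shrinkage of the arm contrast, and the cited framework is not available here. A rule that used the mediator's own coefficient would not see zero: in the simulation it averaged −0.459. That is still diluted, because the slope is averaged over four visits including baseline: −0.6 × 3/4 = −0.45.
- **Missing data.** The contrast can then move slightly.

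All four stand against the stronger claim. None of them says which model will be fitted.

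On timing, it is fair that the SAP also plans the 0-3 month change, which does precede the outcome, and that a 12-month analysis exists with which the 0-6 month change could be paired. The SAP does not make that pairing. The engagement wording may simply be loose: Protocol 9.4.9 can be read as applying change scores to coping and self-efficacy only. The SAP sentence cannot easily be read that way.

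**Conclusion.** The concern holds in limited form. If the mediator is a fixed change score entered as a main effect, baseline is among the repeated outcomes, and the contrast is 6-month change, then the arm effect is exactly unchanged with complete data and essentially unchanged with missing data. Comparing adjusted and unadjusted arm effects could then show no mediation when mediation is total. The cancellation is algebra; the sizes in the table depend on assumed mediator effects.

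Under other readings that the text permits, the share explained under the same total mediation ran from 48% to about 100%. That span, from 0% to about 100% according to an unstated choice, is more than missing detail.

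Independently of the model, order in time is not established for the 0-6 month change in coping and self-efficacy against the 6-month outcome, and the engagement change scores are undefined. The plan should be corrected, but because the analysis is exploratory, neither the primary result nor the secondary treatment comparisons are affected.

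**What to change.** Amend the SAP's Mediation Analysis paragraph as follows.

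1. For the 6-month outcome, use the 0-3 month change in coping and self-efficacy, and 12-week engagement as a level rather than a change. Use the 0-6 month change only for the 12-month outcome, or label it as association only.
2. State whether the mediator is fixed or time-varying and whether baseline pain is a response or a covariate. With a fixed mediator, add a mediator-by-time interaction. Alternatively, regress 6-month pain interference on arm, mediator, baseline pain interference and, where one exists, the baseline mediator value, keeping site and depression group.
3. Define the indirect effect and report it with a confidence interval, with the rule for interpreting it.
4. Confirm the visits at which coping is measured.

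The cost is SAP wording and a little analysis work. No new data are needed if coping is collected as Table 4 shows. Either model still assumes no unmeasured confounding between mediator and outcome, which the report should say.
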